## **I-Abstract**

**Statement of problem:** Light-cured direct zirconia-based composite has many potential uses in dentistry, because of mechanical and biological reasons maintaining the health of peri-implant soft tissues during healing. Direct zirconia-based composite customized healing abutments have superior properties such as biocompatibility, chemical stability, antibacterial and mechanical properties.

**Aim of the study:** This study will be carried out to compare zirconia-based composite customized healing abutments vs conventional composite customized healing abutment placed simultaneously with delayed dental implant placement.

**Materials and Methods:** This will be done by clinical evaluation of peri-implant soft tissue changes. Moreover, peri-implant sulcus fluid (PISF) will be measured for the level of Interleukin-1 beta (IL-1 $\beta$ ) in the gingival crevicular fluid.

## **II. Background**

In the field of dental implantology, healing abutments play a critical role in peri-implant tissue healing and are traditionally designed as prefabricated components, typically made of titanium.

These abutments have been effective but are limited by their cylindrical shape, which may not mimic natural soft tissue profiles, leading to less favorable aesthetic and functional outcomes.

To address these limitations, the use of customized healing abutments as a treatment strategy, was potentially able to give better results in terms of both soft and hard tissues (*Almadani et al., 2023*).

Customized healing abutments can be fabricated by advanced materials like PEEK, PMMA, zirconia, resin composite, and titanium have been explored (*Chokaree et al., 2022*).

Composite materials with nano-zirconium fillers are gaining attention for their ability to combine both biological and mechanical advantages (*Hu et al., 2019*).

Nano-zirconium fillers, embedded within the resin composite matrix, enhance the material's strength, durability, and wear resistance while maintaining its biocompatibility and chemical stability (*Bannunah, 2023*).

Long-term randomized clinical controls have shown excellent soft tissue texture, quality and health when zirconia is used subgingivally and supragingivally and shows a qualitatively improved level of interaction between oral tissues and ceramic dental components made from  $ZrO_2$  (*Kunrath et al., 2021*).

Additionally, these nano-zirconium filler-based composites offer improved aesthetic outcomes due to their tooth-like translucency, making them ideal for anterior regions where appearance is critical.

From a biological perspective, compared to  $TiO_2$  particles,  $ZrO_2$  particles caused reduced toxicity and inflammatory cytokine production (*Ramenzoni et al., 2021*).

Monitoring inflammatory markers like interleukin-1 beta (IL-1 $\beta$ ) can provide valuable insights into the peri-implant tissue response and help compare the performance of these novel materials to traditional titanium healing abutments (*Khatri et al., 2022*).

Understanding the comparative benefits of these materials could inform clinical decisions and improve patient outcomes in dental implant therapies could inform clinical decisions and improve patient outcomes in dental implant therapies.

## **II-Research Question**

*“Do direct zirconia-based composite customized healing abutments have a favorable effect on peri implant soft tissue that may be related to the superior biological properties of zirconium nano particles regarding increased biocompatibility and decreased inflammatory response?”*

### ***PICOTS Elements:***

Patient/Problem	Patients that are eligible for implant placement within inclusion criteria.
Intervention	Zirconia-based composite customized healing abutment.
Comparator	Conventional composite customized healing abutment.
Outcome	Clinical evaluation of peri-implant soft tissue changes via pink esthetic score and papilla index. Biochemical assessment of IL-1 $\beta$ level in the gingival crevicular fluid using Periopaper strip.
Time	Baseline, 1,2 and 3 months after implantation.
Setting	Faculty of Dentistry, Ain Shams University.

## **IV.Aim of the study**

This study will be carried out to compare between direct zirconia-based composite customized healing abutments vs conventional composite customized healing abutments placed simultaneously with delayed dental implant placement.

### **Primary outcome:**

Clinical evaluation of Pink Esthetic Score (PES) and Papilla Index.

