## **VII. Materials and Methods:**

- **Study Setting:** Faculty of Dentistry, Ain Shams University.
- **Sample Size Calculation:** A power analysis was designed to have adequate power to apply a two-sided statistical test of the null hypothesis that there is no difference would be found between different tested groups regarding pink esthetic score. By adopting alpha ( $\alpha$ ) and beta ( $\beta$ ) levels of (0.05) (i.e. power=95%) and an effect size (d) of (1.87) calculated based on the results of a previous study; the total required sample size (n) was found to be (18) cases (i.e., 9 cases per group). Sample size was increased to account for possible dropout during different follow up intervals to be (22) cases (i.e., 11 cases per group). Sample size calculation was performed using R statistical analysis software version 4.3.2 for Windows.
- **Eligibility criteria:**  

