### **Clinical Parameters Included:**

#### **1-Clinical evaluation of soft tissue:**

Pink Esthetic Score (PES) and The Papilla Index will be evaluated and changes between the two groups will be compared at baseline, 1,2 and 3 months (*Almadani et al., 2023*).

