## **IX. Statistical Analysis:**

### **Statistical methods:**

Categorical data will be represented as frequency (n) and percentage (%) and will be analyzed using chi square test. Numerical data will be explored for normality by checking the data distribution, calculating the mean and median values and using Shapiro-Wilk tests. If the data is found to be normally distributed, it will be presented as mean and standard deviation values and independent t-test will be used for the analysis. If the assumption of normality is found to be violated; the data will be presented as median and range values and will be analyzed using Mann-Whitney U test. The significance level will be set at  $p<0.05$  for all tests. Statistical analysis will be performed with R statistical analysis software version 4.3.2 for Windows.

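### Two unranked primary scores are compared at three follow-up visits at 0.05 each, while the sample size covers one PES test at no named visit

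*Protocol*

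**What the plan says.** All of the following is in the Protocol.

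- **Primary outcome:** the whole entry is "Clinical evaluation of Pink Esthetic Score (PES) and Papilla Index". The two scores are joined without an order, a visit or a rule for success. The PICOTS table repeats the pair: "Clinical evaluation of peri-implant soft tissue changes via pink esthetic score and papilla index".
- **Clinical evaluation of soft tissue:** for both scores, "changes between the two groups will be compared at baseline, 1,2 and 3 months". The Time row of the PICOTS table lists the same visits. Neither place makes one visit decisive.
- **Statistical methods:** separate two-group tests (t-test or Mann-Whitney for numerical data, chi-square for categorical data). "The significance level will be set at" 0.05 for every test.
- **Sample Size Calculation:** "A power analysis was designed to have adequate power to apply a two-sided statistical test of the null hypothesis" that "no difference would be found between different tested groups regarding pink esthetic score". Alpha is 0.05, power 95% and d = 1.87. The result is that "the total required sample size (n) was found to be (18) cases (i.e., 9 cases per group"), and then "Sample size was increased to account for possible dropout during different follow up intervals to be (22) cases". No visit is named, and the Papilla Index has no effect size.

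**The concern.** The sample size describes a trial with one primary test. The outcome and assessment sections describe two scores at three post-baseline visits, each tested at 0.05. The Hypothesis entry does not settle the matter, because it speaks of soft-tissue effect in general and names neither score nor visit.

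At least three success rules fit the text:

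1. PES decides, at whichever of the three visits is significant.
2. Any one of the six tests is enough.
3. Both scores must be significant, at a visit that may or may not be named beforehand.

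They carry different false-positive rates. As written, the visit that supports the conclusion, and under the second rule also the score, can be chosen after the data are seen. The Clinical Relevance entry expects the result to influence the standard choice of abutment material, so the error rate behind the primary claim matters.

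**Working it through.** **Inputs from the Protocol.** Two primary scores; three post-baseline visits (1, 2 and 3 months); two-sided alpha 0.05 per test; d = 1.87 for PES; 9 per group evaluable, 11 per group enrolled. Baseline is also listed as a comparison time but is left out here, which keeps the count of tests low.

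**Inputs assumed.** The Protocol gives no correlations between visits or between scores, so 0.5 to 0.9 is used. Both scores are treated as numerical and compared by t-test.

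**Step 1: the plan's own figure.** For a two-sided two-sample t-test, the noncentrality is d × √(n/2) with 2n − 2 degrees of freedom.
- n = 9: 1.87 × √4.5 = 3.97, critical t = 2.120 on 16 df, power 96.1%.
- n = 8: power 93.5%.
- Solving for 95% gives n = 8.53, rounded up to 9 per group, 18 in total.

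The stated 18 reproduces, for exactly one PES test.

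**Step 2: size of the primary family.** 2 scores × 3 visits = 6 tests at 0.05. With independent tests, the chance of at least one false positive is:
- PES at any of three visits: 1 − 0.95³ = 14.3%
- any of six tests: 1 − 0.95⁶ = 26.5%

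**Step 3: correlated tests.** Null trials were simulated (multivariate normal data, pooled t-tests, 11 per arm, no difference on either score).

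| Success rule | Correlation 0.5 | 0.7 | 0.9 |
|---|---|---|---|
| PES, one named visit | 5% | 5% | 5% |
| PES, any of three visits | 12.7% | 11.2% | 8.5% |
| Any of six, one common correlation | 21.2% | 16.8% | 11.1% |
| Any of six, score and visit correlations multiplied | 22.4% | 18.2% | 12.0% |
| Both scores, one named visit | 0.87% | 1.56% | 2.85% |
| Both scores, same but unnamed visit (common / multiplied) | 2.2 / 2.4% | 3.5 / 3.8% | 4.7 / 5.2% |

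The last row sets score and visit correlations equal. When they differ, the rate can pass 5%: 5.6% with score 0.8 and visit 0.5, 6.7% with 0.9 and 0.7, about 7.6% with 0.9 and 0.5, and about 9% with 0.95 and 0.5. Requiring both scores at one named visit cannot exceed 5%, since the joint event is no more likely than either test alone.

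**Step 4: power if both scores stay primary and one is enough.** PES power at d = 1.87 and a flat alpha of 0.025 (Bonferroni) is 92.0% at 9 per arm, 94.9% at 10 and 96.8% at 11. These are lower bounds for Holm, which tests PES at 0.05 once the Papilla Index has passed 0.025. With an assumed Papilla Index d of 1.87 and a correlation between scores of 0.5 to 0.8, Holm power for PES is about 94-95% at 9 per arm and 96-97% at 10.

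**The case against.** **A statistical analysis plan may already settle this.** The decisive visit and the handling of multiplicity are often fixed there, and it is not at hand. That stands as a limit: nothing here shows that the trial has no rule. But the protocol is not merely silent. It makes two scores primary side by side, lists the visits and sets 0.05 for all tests, against a sample size for one test. That mismatch lies in the protocol.

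**PES may be meant to lead, since the trial is sized on it.** This is the most natural reading, and the conclusion is led by it. The Primary outcome entry does not say so, however, and three visits would still remain.

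**The percentages are illustrative.** This is fair. The correlations are assumed, and the Papilla Index is a 0-4 scale that may go to Mann-Whitney or chi-square. Heavily tied data at 11 per arm were not examined.

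**Stronger conclusions that a reader might infer, and that do not hold:**
- *The trial carries a 26.5% false-positive risk.* No section says that any one of six results is enough, and independence is implausible: visits repeat on the same patients, and the PES table itself contains mesial and distal papilla items. The figure is an upper bound.
- *Requiring both scores at the same visit is safe in any case.* It is safe only if the visit is named.
- *Keeping both scores primary under Holm uses up the dropout allowance or needs a larger trial.* The flat-0.025 figures understate Holm when the Papilla Index also differs. If one score is enough, the Papilla Index does not need 95% power of its own.

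**Conclusion.** The concern holds, and should be settled before outcomes are seen. The protocol's 5% alpha and 95% power belong to one PES test at one visit, and the protocol does not name that visit or give PES sole primary status. With no difference on either score, the chance of a false-positive primary claim is about 8-13% if PES may succeed at any of three visits (14.3% if independent) and about 11-22% if any of six tests counts. Requiring both scores at one named visit keeps it at or below 5%; at the same but unnamed visit it is about 2-9%, depending on how score and visit correlations differ.

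These sizes rest on assumed correlations, t-tests and 11 per arm, and on the visit or score being chosen after the results are known. That some inflation exists under the first two rules does not depend on the exact correlation, unless the tests are perfectly correlated. A reader might infer that the sample size is miscalculated; it is not, since 9 per group is right for the single test it describes.

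**What to change.** **Preferred.** Before outcomes are seen, state in the protocol: *The primary outcome is the PES total at [one prespecified visit, chosen by the investigator], compared between groups once at two-sided 0.05.* Add that the Papilla Index and the other PES visits are secondary, are reported with estimates and 95% confidence intervals, and are not used to declare success.

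This takes two sentences and no extra patients. Power at 9 per group stays at 96.1% for d = 1.87, and the allowance of four dropouts (22 − 18) is untouched. The downside is small: the secondary comparisons can no longer carry the primary claim.

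**If both scores stay primary.** Name one visit and say whether one or both must be significant.
- *One is enough:* use Holm over the two tests and restate the power. The flat-0.025 values above are the floor for PES; any higher figure needs a stated effect size for the Papilla Index.
- *Both are required:* no alpha adjustment is needed, but power cannot be stated until the protocol gives an effect size for the Papilla Index.

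If a statistical analysis plan already fixes the outcome, visit and rule, carry the same wording into the protocol.

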### **Secondary outcome:**

Determine the impact of the customized healing abutment on the level of Interleukin-1 beta (IL-1 $\beta$ ) in the gingival crevicular fluid.

### **Clinical Relevance:**

The result will affect the gold standard in choosing the customized healing abutment material for implant patients, regarding which one offers better peri-implant soft tissue results, healing stimulation, and less inflammatory response.

- **Hypothesis:**

Direct zirconia-based composite customized healing abutments do not have a significantly different effect on peri-implant soft tissue compared to conventional composite customized healing abutment in terms of biological properties or biocompatibility or inflammatory response.

## **VI. Ethical consideration**

- **Risk and discomfort of patients:** This research will be conducted with consideration of patient safety and with attempts to reduce discomfort to patient, risks include postoperative pain, edema that can be controlled with medication.
- **Minimization of the risk:** Patient baseline vitals will be taken before any medical procedure to ensure patients safety. Moreover, all medical operation will be conduct under standardized infection control procedure.
- **Criteria for Discontinuation of Study/patient:** patient will be allowed to leave study if developed any complications either related to the study intervention or related to the general condition of the patient. The patient will have the right to withdraw from the study at any time.
- **Benefits to the Patients and to the Community:** patients will receive an aesthetically and functionally implant with no cost. The community will benefit from this study by having a wider range of healing abutments to choose from.
- **Privacy:** All patients identification including patient data and pictures will be locked and not shared.
- **Confidentiality:** patient's data will be treated with utmost confidentiality. In which no personal other than the researchers will be able to view the patient's data.
- **Data Management:** All patient's data will be saved on researcher's personal laptop that are not connected to any intranet connections and no copies will be made in any kind of database.
- **Consent Procedures if Applicable:** any medical procedures and photographs will have a printed written consent form.
- **Patient Informed Consent Form:** a proper consent form will be formulated & signed by the patient before starting any procedure.

## **VII. Study Design:**

Randomized, controlled, parallel design, two arms clinical trial.

## **VII. Materials and Methods:**

- **Study Setting:** Faculty of Dentistry, Ain Shams University.
- **Sample Size Calculation:** A power analysis was designed to have adequate power to apply a two-sided statistical test of the null hypothesis that there is no difference would be found between different tested groups regarding pink esthetic score. By adopting alpha ( $\alpha$ ) and beta ( $\beta$ ) levels of (0.05) (i.e. power=95%) and an effect size (d) of (1.87) calculated based on the results of a previous study; the total required sample size (n) was found to be (18) cases (i.e., 9 cases per group). Sample size was increased to account for possible dropout during different follow up intervals to be (22) cases (i.e., 11 cases per group). Sample size calculation was performed using R statistical analysis software version 4.3.2 for Windows.
- **Eligibility criteria:**  
**Inclusion Criteria:**
  1. Patients should be systematically free from any disease as according to Cornell Medical Index-Health Questionnaire (**Pendleton et al., 2004**).
  2. Both genders.
  3. Age from 20-50 years.
  4. Missing tooth to be restored with standard implant, with no need for additional bone and soft tissue augmentation procedures (**Beretta et al., 2019**).
  5. Implants primary stability ISQ  $\geq$  70 unites using the Osstell Mentor (**Baltayan et al., 2016**).
  6. Sound Mesial and distal neighboring teeth.
  7. At least 6 natural teeth remaining in the same arch .
  8. Mouth opening  $\geq$  30mm.
  9. Thick phenotype.

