### **Study procedures:**

**1- Randomization and allocation concealment technique:** Patients will be randomly allocated according to predetermined computer-generated randomization using [www.Randomizer.org](http://www.Randomizer.org)

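### Anterior and posterior sites are pooled for aesthetic primary scores with no stratification or adjustment by region, which costs precision and risks chance imbalance between arms of 11

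*Protocol*

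**What the plan says.** **Eligibility** (Protocol, Inclusion Criteria). Criterion 4 reads "Missing tooth to be restored with standard implant, with no need for additional bone and soft tissue augmentation procedures". Criterion 6 reads "Sound Mesial and distal neighboring teeth". No inclusion or exclusion criterion names a region, arch or tooth type.

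**Primary outcome** (section IV): "Clinical evaluation of Pink Esthetic Score (PES) and Papilla Index". The PES table grades both papillae, tissue contour, gingival level, alveolar process, colour and texture. The Papilla Index grades papilla fill.

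**Region in the rationale** (section II, Background). One sentence describes zirconium-filled composites as "making them ideal for anterior regions where appearance is critical".

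**Allocation** (Study procedures, item 1): "Patients will be randomly allocated according to predetermined computer-generated randomization using" a named website. No stratification factor is given.

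**Sample size** (section VII). A two-sided test of PES with "levels of (0.05) (i.e. power=95%) and an effect size (d) of (1.87) calculated based on the results of a previous study" gives 18 cases, 9 per group, raised to 22, 11 per group, for dropout.

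**Analysis** (section IX). Numerical data go to an independent t-test, or to a Mann-Whitney U test if normality fails. Neither includes a covariate.

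**The concern.** Tooth position plausibly affects papilla fill, contour and ridge form whatever the healing abutment is made of. It is known before allocation, from the screening examination and CBCT. The Protocol already narrows other local sources of variation (thick phenotype, a minimum stability reading, sound neighbours, no augmentation), but it neither balances position at allocation nor accounts for it in the comparison.

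Two consequences follow from the same between-region variance. In an unadjusted comparison it widens the spread of the scores. In the one trial that is run, arms this small may by chance differ in site mix, so that part of the observed PES difference reflects where the implants were placed. A stratified allocation would prevent the second, and it cannot be introduced after enrolment.

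**Working it through.** **1. The plan's own figure.** Inputs from section VII: two-sided alpha 0.05, power 95%, d = 1.87. Using the noncentral t with 2n − 2 degrees of freedom and noncentrality d·√(n/2), power is 93.5% at 8 per arm and 96.1% at 9. The stated 18 therefore reproduces and is not disputed. At the enrolled 11 per arm, power is 98.6%.

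**2. Chance imbalance.** Let K be the number of anterior sites among 22 (assumed; the Protocol gives no mix), with arms fixed at 11:11. The number x of anterior sites in one arm is hypergeometric:

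P(x) = C(K, x)·C(22 − K, 11 − x) / C(22, 11), with C(22, 11) = 705,432.

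For K = 11, the terms for x = 7 to 11 are 330², 165², 55², 11² and 1², which sum to 139,272. Then 2 × 139,272 / 705,432 = 0.395. From x = 8 upward the sum is 30,372, giving 0.086.

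| Anterior sites K (assumed) | Imbalance | Probability |
|---|---|---|
| 6 | 5 v 1 or worse | 14.9% |
| 8 | 6 v 2 or worse | 18.3% |
| 11 | 7 v 4 or worse | 39.5% |
| 11 | 8 v 3 or worse | 8.6% |
| 14 | 9 v 5 or worse | 18.3% |

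The count difference has the same parity as K. For even K, a difference of 3 or more therefore means 4 or more, which is why those rows are lower. Over K = 6 to 14 the probability of a difference of at least 3 runs from about 15% to 40%.

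**3. Effect of a 7-v-4 split.** Let s be the difference in mean PES between regions, in within-region SD (assumed, 0.5 to 2). With no material effect, the arm difference moves by (7/11 − 4/11)·s = 0.273·s. That is 0.14, 0.27, 0.41 and 0.55 SD for s = 0.5, 1, 1.5 and 2. Against the design effect of 1.87, the range is 0.14/1.87 = 7% to 0.55/1.87 = 29%.

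**4. Effect of pooling on power.** If 1.87 is a within-region effect and the mix is 50:50 (both assumed), the pooled SD is √(1 + 0.25·s²) times the within-region SD, and the effective d is 1.87 divided by that factor.

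| s | SD factor | Effective d | Power, 9 per arm | Power, 11 per arm |
|---|---|---|---|---|
| 0 | 1 | 1.87 | 96.1% | 98.6% |
| 0.5 | 1.031 | 1.814 | 95.0% | 98.1% |
| 1 | 1.118 | 1.673 | 91.4% | 96.1% |
| 1.5 | 1.250 | 1.496 | 84.6% | 91.6% |
| 2 | 1.414 | 1.322 | 75.0% | 83.9% |

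**5. Type I error.** Simulating 11 of 22 sites anterior, a 1.5 SD region gap and no treatment effect, the unadjusted t-test rejects in about 5.0% of trials.

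Steps 3 and 4 are two views of one source of variance and must not be added together.

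**The case against.** Broad eligibility with unstratified randomisation is a legitimate design, and a valid test already allows for chance imbalance. That stands. A reader might infer that the result would be systematically biased or the false-positive rate inflated; step 5 of the working shows otherwise.

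A reader might also infer that any arch position qualifies. It does not: the need for a tooth on each side rules out terminal gaps, and the phenotype, stability and no-augmentation criteria narrow the sites further.

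Nor do the documents support saying that the rationale is anterior, so that posterior sites do not belong. The Background has a single supporting sentence on anterior appearance, while the research question and hypothesis concern soft tissue, biocompatibility and inflammation without limit by region.

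The scales are partly relative to the site: several PES items grade a difference, and the Papilla Index grades fill of the available space. The clinical parameters section also speaks loosely of comparing changes from a baseline. If change scores are what is analysed, some of a fixed site effect drops out, which favours the lower end of the ranges.

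The site mix and region effect are not in the Protocol. The power loss also requires 1.87 to be a within-region value, and the source study is not available.

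Finally, a separate SAP could add region to the analysis. It could not add stratification to an allocation already made. The absence of stratification is read from what the randomisation paragraph leaves unnamed; it is not stated outright.

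**Conclusion.** The point holds as a cheap gain in precision and balance. Anterior and posterior bounded sites are both eligible, no stratification factor is named, and the stated tests are unadjusted.

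The size is conditional. The chance of a count difference of 3 or more is about 15% to 40% if 6 to 14 of 22 sites are anterior. A 7-v-4 split shifts the arm difference by 0.14 to 0.55 SD if region moves PES by 0.5 to 2 within-region SD. Over the same range, a 50:50 mix puts power at 95% to 75% with 9 per arm, or 98% to 84% with all 11 retained, provided that d = 1.87 is a within-region value. If the source study pooled sites, the stated power already reflects the wider spread and nothing is lost against it, although adjustment would still gain precision.

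The trial is not invalid, and the sample size calculation is not in error.

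**What to change.** **Study procedures, item 1.** Stratify the computer-generated list by region (anterior or posterior, classified from the screening examination and CBCT before allocation). Use small, randomly varied block sizes and conceal the list from the enrolling clinician. Concealment matters here because only the data analysts are blinded and the paragraph describes no concealment mechanism; short fixed blocks could be guessed.

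**Section IX.** Include region as a factor in the PES and Papilla Index comparison: a linear model with arm and region where normality is acceptable, and a region-stratified rank test such as van Elteren's in place of the Mann-Whitney U test where it is not.

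**Cost.** One further list and one degree of freedom (at 9 per arm, 16 becomes 15). The regional imbalance is held to about one or two sites. Incomplete last blocks may leave the arms off 11:11 by a patient or so. Some predictability of short blocks remains, limited by varying and concealing them. No extra patients, visits or staff are needed, and eligibility need not be restricted.
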